1.0 GENERAL INFORMATION

This document is a clinical research protocol and the described study will be conducted in compliance with the IRB approved protocol, associated Federal regulations and all applicable IRB requirements. Pilot data collected from this feasibility study will support a novel R21 application to assess the efficacy of an online group sessions and eHealth communication intervention in a rural population of Latino adults with hypertension, diabetes, cardiovascular disease, cancer, and/or obesity via a feasibility assessment. Importantly, through collaboration with community partners, the current and subsequent trials will build community capacity to deliver nutrition and PA resources to underserved rural Latino adults and to introduce innovative technology-based intervention strategies not often applied in rural Latino communities.

Testing scalable intervention strategies for uptake of nutrition and PA recommendations as a new treatment model to improve cardiometabolic health with potential for broad dissemination among Latinos living in a rural community. This feasibility study will generate preliminary data needed to design a novel R21 proposal for a larger trial with long-term outcomes in a broad population of Latino adults living in a rural setting. We will leverage the Fred Hutch capacity and resources to provide rural adult Latinos with tools beyond brochures and single visit referrals to clinicians to discuss lifestyle modifications. This work has the potential to identify a scalable and cost-effective intervention targeting multiple lifestyle behaviors to be disseminated in clinical and community settings.

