In October 2021, investigation into the reason for slow recruitment (n=22 to date) revealed a high burden of data collection for potential participants. In addition, preliminary analyses of data currently being collected by [name] in a similar intervention among a predominantly non-Hispanic white population of urban breast cancer survivors suggested a minimal effect of the low dose arm. As such, Drs. [name] and [name] decided to adapt the study as follows: change the design to be a single-arm feasibility study in which all participants receive the full “high-dose” intervention, decrease the target recruitment goal, and decrease participant burden by removing intensive data collection methods. These modifications will yield valuable information to determine how best to proceed with future diet and physical activity behavioral interventions in this rural population.

Overview of Study Design. The proposed pilot study will recruit 25 Latinos who are residents of the rural Lower Yakima Valley (LYV) with one or more of the following diagnoses based upon self-report: hypertension, diabetes, cardiovascular disease, obesity, or a history of cancer. Recruitment, retention, and data collection procedures will be carried out by Community Health Educator (CHE) study staff. Eligible participants will undergo online baseline assessments over a period of 1-2 weeks. Interested and eligible participants will be sent an online informed consent, HIPPA and medical records release form and baseline questionnaires to complete.

Following the completion of baseline data collection, participants will receive the intervention. All participants will receive a Fitbit device to self-monitor their PA. The intervention will include 6 biweekly 2-hour Zoom-based nutrition, culinary, and physical activity sessions. The sessions will be led by a local chef consultant and CHE, both trained by the study team. Participants will receive eHealth communication meant to motivate healthy diet and improved PA via educational and motivating text messages and using resources available as part of the study-related website over a 3-month period. Following completion of the 3-month intervention period, repeated baseline at-home assessments will take place and an exit intervention completed. The exit interview will include questions regarding acceptability and accessibility of the intervention for participants.

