2.3 Risks/Benefits

There are few potential risks that may occur to participants. There may be some discomfort in completing questionnaires about cancer and other diseases, but staff are trained to be aware of such discomfort and are trained to be compassionate to individuals answering such questions. Research related injuries are highly unlikely due to the low risk nature of this study; however, there is a risk of unintentional injuries that may occur while cooking, dancing or participating in exercises as promoted via online sessions. Participants will be asked to increase their physical activity during the 3 months of the study. This increased physical activity may cause unintentional soreness, joint pain or exercise related injuries. Recommended dietary changes may include gas and bloating due to increased fiber consumption. The timing and frequency of the online sessions and data collection at baseline and 3 months may provide an inconvenience to participants' schedules.

Participants will receive up to \$50 in compensation in the form of a gift card to a local vendor. Since the in-person session are to be delivered via online Zoom videos, we are also providing participants randomized to receiving the online sessions with a grocery bags with an estimated cost of \$25 or less per sessions for total of \$150 in groceries per participant to cover all six sessions or one session. Aside from the gift card and grocery bags and gaining new knowledge about ways in which participants can decrease their risk of cancer reoccurrence by being physically active and consuming a diet high in fruits and vegetables and low in fat and added sugar, there are no other direct benefits of this research to a given study participant. The data from the study will be used to direct future intervention efforts targeting similar populations.

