3.3 Study Design

This is a single arm feasibility study to assess a culturally tailored eHealth diet and physical activity program for rural Latino adults with a history of hypertension, diabetes, cardiovascular disease, cancer, and/or obesity in the Lower Yakima Valley.

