Resources for cooking component of online sessions: All participants (n=25) will be provided with a grocery bag with the ingredients needed to participate in the hands-on cooking portion of the online sessions. Study staff will arrange the purchasing of the ingredients and will offer participants with the option to pick up the grocery bag at a convenient local grocery store or to have it delivery to participants homes either via Instacart or similar delivery service and/or by study staff, if needed. The total cost of each grocery bag is estimated at \$25 or less per session for a recipe to serve 4 or more. The ingredients provided will be based on each menu to be demonstrated by the trained Chef so participants can prepare the meals themselves at home. Once the grocery

bags are ready for pick-up or delivery, depending on participants preference, study staff will send a friendly reminder to participants and will help coordinate as needed.

Fidelity of the online group-based intervention will be assessed by an objective process evaluator, who will attend all sessions and observe and take detailed notes on the timing of the activities and delivery according to protocol. This person will not have any interaction with study participants and will not participate in data collection or study activities implementation.

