13.0 STATISTICAL CONSIDERATIONS

13.1 Study Design

This is a single-arm feasibility assessment.

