13.2 Primary/Secondary Endpoints/Hypotheses and Analytical Methods

The endpoints for Aim 1, feasibility of intervention strategies, include accrual rate, adherence, retention, and acceptability (exit interview). Adherence will be measured by attendance to online sessions, text message responses, and use of the website. Retention will be measured by completion of all study assessments.

Acceptability will be measured on a Likert scale in each of a series of questions regarding various aspects of the trial during the exit interview. All endpoints will be summarized using descriptive statistics. Statistical differences in retention rates for each study assessment between study arms will be assessed by Chi-square tests, and acceptability by t-test of median per-patient scores.

Exploratory endpoints include changes in anthropometrics, mediators of behavior change, and patient-reported psychosocial/quality of life outcomes. Descriptive analyses will be conducted to summarize exploratory outcomes.

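### Section 13.2 plans between-arm tests of retention and acceptability in a study that now has one arm and no control

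*Combined protocol and SAP*

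**What the plan says.** The current design has one arm. Section 1.0 records the October 2021 decision to "change the design to be a single-arm feasibility study in which all participants receive the full" high-dose intervention. Section 3.3 repeats it: "This is a single arm feasibility study to assess a culturally tailored eHealth diet and physical activity program". Section 13.1 says "This is a single-arm feasibility assessment". The synopsis gives the treatment groups as single-arm, the control as not applicable and the sample size as 25.

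Section 13.2 first says that all endpoints will be summarised descriptively. It then adds: "Statistical differences in retention rates for each study assessment between study arms will be assessed by Chi-square tests, and acceptability by t-test", with the t-test applied to each patient's median score. Section 3.3.1 lists retention and acceptability among the primary endpoints.

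Four other places keep two-arm wording:

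- The synopsis gives the trial type as a pilot RCT.
- Section 2.3 speaks of "providing participants randomized to receiving the online sessions with a grocery bags", with a total of $150 "per participant to cover all six sessions or one session". Section 6.2 says instead: "All participants (n=25) will be provided with a grocery bag with the ingredients needed".
- Section 6.4 sends text messages to participants in both arms.
- Section 12.0, under Website, promises archived recordings to people randomised to low dose.

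**The concern.** A comparison between arms needs at least two arms. If the study has one, the only formal tests planned for two primary endpoints have no comparator.

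An analyst following Section 13.2 literally would have to depart from the protocol or make up a comparator. The second course carries the greater risk, because a split of about 25 people chosen after the data are in could be presented as the prespecified test.

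The stated purpose also points elsewhere. Section 1.0 says: "This feasibility study will generate preliminary data needed to design a novel R21 proposal for a larger trial". What a later trial needs from this one is an estimate of retention and its precision. Section 13.2 does not say that precision will be reported.

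**Working it through.** **Inputs.** Number of arms: 1 (synopsis; Sections 1.0, 3.3 and 13.1). Control: none (synopsis). Sample size: 25 (synopsis; Section 1.0). Tests: chi-square for retention and t-test for acceptability (Section 13.2). Significance level, power, effect size, expected retention and null value: not given. There is therefore no calculation behind the figure of 25 to reproduce.

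**Chi-square test.** Degrees of freedom are (rows − 1) × (columns − 1). With one arm and two outcomes (retained or not), this is (1 − 1) × (2 − 1) = 0. For an illustrative 20 retained and 5 not, the expected counts equal the observed counts (20 and 5), so the statistic is 0 and p = 1. The same happens for any split of the 25, so the result carries no information.

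**t-test.** A two-sample test needs a second group, and there is none. A one-sample test needs a null value, and none is stated. Grammatically the clause continues the comparison between arms.

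**Other possible comparators.**

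- *By former arm.* Section 1.0 reports 22 people recruited by October 2021. It does not say whether any had been allocated to an arm, and no comparison by former arm is planned.
- *Historical control.* None is named.

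**What one arm of 25 can report.** The exact (Clopper-Pearson) 95% limits for x retained out of n are:

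- lower = 0.025 quantile of Beta(x, n − x + 1)
- upper = 0.975 quantile of Beta(x + 1, n − x)

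The documents give no expected retention, so the counts below are assumed.

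| Retained | Proportion | Exact 95% CI | Width (points) |
|---|---|---|---|
| 15/25 | 60% | 38.7% to 78.9% | 40.2 |
| 18/25 | 72% | 50.6% to 87.9% | 37.3 |
| 20/25 | 80% | 59.3% to 93.2% | 33.9 |
| 22/25 | 88% | 68.8% to 97.5% | 28.7 |
| 23/25 | 92% | 74.0% to 99.0% | 25.0 |
| 25/25 | 100% | 86.3% to 100% | 13.7 |

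**Groceries in Section 2.3.** Six sessions at $25 give $150, and one session gives $25. The stated $150 fits only the six-session programme, so the one-session alternative belongs to the dropped low-dose arm.

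**The case against.** The strongest reply is that this is one leftover sentence with little consequence. The sentence before it already commits to descriptive statistics for every endpoint, the single-arm intent is stated in several places, and no alpha, power, sample size or decision rule rests on the tests. If the sentence were ignored, the feasibility results would still be produced. This stands, and it limits how serious the point is.

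It is also fair that both tests fail for one reason, the lost second arm, and should not be counted as two independent faults. The confidence interval is an improvement: the documents set no precision target, and descriptive statistics do not exclude an interval.

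A further point concerns the 22 people recruited before the redesign. If any had been assigned to low dose, removing the archive sentence in Section 12.0 could withdraw something they were promised. If any had started the heavier assessment set, completion of all assessments would not mean the same thing for everyone. Section 1.0 describes the two-arm plan in conditional terms, which suggests that nobody was allocated but does not settle it. Their status should be confirmed before the edits are made.

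None of this gives the tests a comparator. The sentence is current analysis text, not part of a change history, and it contradicts the section immediately above it.

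**Conclusion.** The concern holds: the sentence is wrong as written. Both hypothesis tests named in the document (2 of 2) concern primary endpoints and cannot be carried out under the current design. The conclusion follows from the text alone and needs no assumed figure.

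The consequence is limited, for the reasons conceded above. The plan should be corrected, but the study's ability to report feasibility is not threatened. The interval widths (about 34 points at 20/25, about 29 at 22/25) rest on assumed counts and show only what a one-sample report would look like.

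**What to change.** Delete the sentence on between-arm tests in Section 13.2 and replace it with text such as:

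> For each study assessment, and for completion of every assessment, retention will be given as the number completing over the number enrolled, with an exact 95% confidence interval. Acceptability will be described by the median and interquartile range of the per-participant scores.

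The documents do not state a denominator for retention. Number enrolled is the proposal here, and the sponsor should confirm it.

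Confirm and record whether any of the 22 people recruited by October 2021 were allocated to an arm or began the earlier assessments. Then correct the remaining wording:

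- Synopsis: replace the pilot RCT label with single-arm feasibility study.
- Section 2.3: remove the reference to randomisation and the one-session alternative, to agree with Section 6.2.
- Section 6.4: replace both arms with all participants.
- Section 12.0, Website: remove the low-dose archive sentence, unless someone was in fact assigned to low dose.

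The single-arm labels in Section 3.3.1 (intervention arm) and Section 6.3 (Arm A) can stay; changing them is optional.

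The cost is wording edits in five places and one exact interval per retention proportion. No data, visits or participants are added, and no usable analysis is lost.

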13.3 Additional Outcome Measures and Statistical Methods

Demographic and clinical characteristics will be measured via an online questionnaire on demographics, comorbid conditions, medical history, and medication use (baseline only).

Intervention feasibility will be measured by accrual, adherence (attendance to online group sessions, response to text messages, and use of website), acceptability of the interventions (exit interview and motivation interviewing educator interaction, MIMSI), quantitative data collection processes (percent completed and duration of staff assistance to complete surveys), and qualitative (exit interviews) data, and retention at 3 months. MIMSI will be administered prior to the exit interview. Exit interviews will be conducted by *promotoras* and audio- recorded and later transcribed for analyses. Feasibility of intervention delivery for staff within in the

rural community context will also be assessed and necessary adaptations from the urban intervention delivery process will be documented.

13.4 Ethnic and Gender Distribution Chart

Projected Target Accrual
ETHNIC AND GENDER DISTRIBUTION CHART

TARGETED / PLANNED ENROLLMENT: Number of Subjects			
Ethnic Category	Sex / Gender		
	Females	Males	Total
Hispanic or Latino	15	10	25
Not Hispanic or Latino	0	0	0
Ethnic Category Total of All Subjects*	15	10	25
Racial Categories			
American Indian / Alaska Native			
Asian			
Native Hawaiian or Other Pacific Islander			
Black or African American			
White	13	8	21
More Than One Race	2	2	4
Racial Categories: Total of All Subjects*	15	10	25

14.0 INVESTIGATOR OBLIGATIONS

The PI is responsible for the conduct of the clinical trial at the site and is responsible for personally overseeing the treatment of all study subjects. The PI must assure that all study site personnel, including sub-Investigators and other study staff members, adhere to the study protocol and to all applicable regulations and guidelines regarding clinical trials both during and after study completion.

All subjects are informed of the nature of the program, its possible hazards, and their right to withdraw at any time, and each subject signs a form indicating their consent to participate prior to receiving any study-related procedures (see Appendix B).

